4.2 Exclusion Criteria

4.2.1 Exclusion Criteria for Focus Groups with Youth (15-20 years old)

- Does not self-identify as trans feminine, trans masculine or gender non-conforming OR birth sex and current gender match;
- Younger than 15 years of age or over 20 years of age;
- Does not report sex with another person in the previous 12 months;
- Does not self-report a HIV negative serostatus.
- Doesn't live in the area or is unable to meet with research staff at either the Baylor College of Medicine (BCM) Adolescent Medicine Trials Unit in Houston, Children's Hospital of Philadelphia, Children's Hospital Los Angeles, the Center for HIV Educational Studies and Training (CHEST) in New York City ;
- Does not have a mobile device with SMS and Internet access capabilities;
- Not English-speaking and/or does not read English (since the intervention will be built in English);
- Unwilling or unable to comply with protocol requirements;
- Unable to understand the Informed Consent/Assent Form.

4.2.2 Exclusion Criteria for Focus Groups with Young Adults (21-24 years old)

- Does not self-identify as trans feminine, trans masculine or gender non-conforming OR birth sex and current gender match;
- Younger than 21 years of age or over 24 years of age;
- Does not report vaginal or anal sex (either insertive or receptive; excluding sex toys) with another person in the previous 12 months.

- Does not live in the area or is unable to meet with research staff at either the Baylor College of Medicine (BCM) Adolescent Medicine Trials Unit in Houston, Children's Hospital of Philadelphia, Children's Hospital Los Angeles, the Center for HIV Educational Studies and Training (CHEST) in New York City;
- Does not have a mobile device with SMS and Internet access capabilities;
- Not English-speaking and/or does not read English (since the intervention will be built in English);
- Unwilling or unable to comply with protocol requirements;
- Unable to understand the Informed Consent/Assent Form.

4.2.3 Exclusion Criteria for Randomized Controlled Trial

- Does not self-identify as trans feminine, trans masculine or gender non-conforming OR birth sex and current gender match;
- Younger than 15 years of age or over 24 years of age;
- Does not report vaginal or anal sex (either insertive or receptive; excluding sex toys) with another person in the previous 12 months.
- Reactive or indeterminate HIV test;
- Unable to meet in person or online with research staff at the Baylor College of Medicine (BCM) Adolescent Medicine Trials Unit in Houston, Children's Hospital of Philadelphia, Children's Hospital Los Angeles, PRIDE Health Research Consortium in New York City, or the Fenway Institute in Boston for the Baseline and 3 month assessment;
- Does not have a mobile device with SMS (text messaging) and Internet access capabilities;
- Not English-speaking and/or does not read English (since the intervention will be built in English);
- Unwilling or unable to comply with protocol requirements;
- Unable to understand the Informed Consent/Assent Form.

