QNS	Query and Notification System
RCG	Radiant Creative Group
RCT	Randomized Controlled Trial
RDC	Remote Data Capture
SRV	Subject Recruitment Venue
SSL	Secure Sockets Layer
TC	Technology Core
Trans	transgender feminine, transgender masculine, gender non-conforming
TWM	Thrive With Me
UMN	University of Minnesota
VL	Viral Load
YAB	Youth Advisory Board
YLWH	Youth Living With HIV
YO	Years Old
YT	Youth Thrive
YYA	Youth and Young Adults

STUDY ABSTRACT

DESIGN:	TechStep is a three-arm, technology-based randomized controlled trial (RCT), with a stepped care approach, among high-risk HIV-negative trans youth and young adults (YYA) for reducing sexual risk behaviors and increasing PrEP uptake.
DURATION:	Trans YYA are enrolled for 9 months in the RCT.
SAMPLE SIZE:	Total study sample is 355 of which the following will be enrolled for each phase: 1) up to 80 participants for focus groups to inform intervention adaption; 2) 275 participants for a randomized controlled trial of TechStep, with participants randomized to either text messaging stepped care (n=108), WebApp stepped care (n=83) or control (n=83) condition.
POPULATION:	Participants will include YYA who are self-identified trans feminine, trans masculine or gender non-conforming or whose birth sex and current gender do not match; ages 15 to 24 years; HIV-negative; and sexually active. For Phase 1, participants must self-report never having received a positive HIV test result; participants age 15-20 must report any kind of sex in the previous 12 months, while participants age 21-24 must report vaginal or anal sex (either insertive or receptive; excluding sex toys) in the previous 12 months. For Phase 2, participants must have a confirmed HIV negative serostatus and report anal or vaginal sex (either insertive or receptive; excluding sex toys) in the previous 12 months. For Phase 2, participants will be recruited from SRVs in Houston, Los Angeles, New York City, Philadelphia, and Boston.
STRATIFICATION:	Focus group discussions will be stratified by age (50% 15-20 years old; 50% 21-24 years old).
DATA COLLECTION:	Focus group discussions will be conducted in-person, digitally recorded, and professionally transcribed. There will be five data collection (screening, baseline, 3-month, 6-month, and 9-month) time points for the RCT. Visits will

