4.1.3 Inclusion Criteria for Randomized Controlled Trial Inclusion Criteria

- Self-identified as trans feminine, trans masculine or gender non-conforming OR birth sex and current gender differ;

- Between the ages of 15 to 24 years old;
- Report vaginal or anal sex (either insertive or receptive; excluding sex toys) with another person in the previous 12 months;
- Negative HIV test;
- Availability to meet with research staff in person or online at the Baylor College of Medicine (BCM) Adolescent Medicine Trials Unit in Houston, Children's Hospital of Philadelphia, Children's Hospital Los Angeles, PRIDE Health Research Consortium New York City, or the Fenway Institute in Boston;
- Have a mobile device with SMS (text messaging) and Internet access capabilities; and
- Read and speak English (since the intervention will be built in English).

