4.4 Screening

All potential participants (whether recruited online, in-person or over the phone) will complete an online screening survey to obtain consent/assent to be screened and verify all inclusion criteria. Screening may occur on the same day as enrollment or beforehand. The online screening survey will begin with a script that will be read by participants to explain the purpose of screening and clarify that if they are eligible, they will be invited to participate in the study. The script will also provide general information about the research study, the nature of the screening questions and related potential risks, the approximate length of the screening (~5 minutes), the confidentiality of the screening information, the use of any screening information obtained, the ability to skip any questions or withdraw at any time, and contact information of key study personnel. After reading this screening script, participants will be asked if they are interested in participating and agree to voluntarily complete the screening procedure. Participants will electronically indicate their agreement and then take the screening survey.

SRV staff may also screen participants using the online screener in person, over the phone, or over a teleconferencing platform such as Zoom or a comparable platform. The SRV staff will obtain verbal consent from the participant to screen, read the screening questions from the online survey to the participant, and record the participant's responses in the online screener.

The online survey is hosted on Alchemer and we will use SSL encryption for transfers of information online and data will be stored in the secure, HIPAA-compliant servers of Alchemer. The Emory AC team maintains a business partner HIPAA agreement with Alchemer. For those who meet eligibility criteria, the survey will ask if they are willing to provide their first name, e-mail, and a phone number. Potential participants who do not meet eligibility criteria will be asked if they would like to be contacted about other research studies and, if so, to provide contact information.

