The Analytic Core will securely share the contact information of eligible participants with SRV sites via a secure Box or Microsoft OneDrive account. SRV staff will enter the eligible participant into SMART for scheduling and contact participants to schedule an in-person visit at the SRV or an online enrollment visit. Study staff also have the option of scheduling and completing some study visit activities in person and some of the study visit activities online to provide flexibility during the COVID-19 pandemic and afterwards and to be responsive to participant needs.

YYA who screen eligible and provide contact information will be contacted by SRV staff and provided with information about the date and time of the focus group (in Phase 1) or to schedule an in person or online baseline enrollment visit (in Phase 2). An email will be sent to potential focus group participants immediately after they are scheduled for the focus group that includes the focus group date, time, location and staff contact information. Potential focus group participants will be sent a reminder three days prior to the focus group, as well as on the day of the focus group.

YYA who screen ineligible (see section 4.2 for exclusion criteria) will be informed at the conclusion of the screener that they are not eligible for the study.

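### The gender exclusion bullet in 4.2.3 (and 4.2.1, 4.2.2) uses OR where negating the either/or inclusion rule needs AND, so people who qualify by one route are both included and excluded

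*Combined protocol and SAP*

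**What the plan says.** The RCT inclusion list in section 4.1.3 opens with an either/or condition: "Self-identified as trans feminine, trans masculine or gender non-conforming OR birth sex and current gender differ". Sections 4.1.1 and 4.1.2 use the same condition for the two focus-group age strata. The Study Abstract describes the overall population in the same way, as people who are "self-identified trans feminine, trans masculine or gender non-conforming or whose birth sex and current gender do not match".

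The first bullet of the RCT exclusion list in section 4.2.3 reads: "Does not self-identify as trans feminine, trans masculine or gender non-conforming OR birth sex and current gender match". The first bullets of 4.2.1 and 4.2.2 carry the same wording for the focus groups.

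Section 4.4 refers to both kinds of list. All potential participants are to "complete an online screening survey to obtain consent/assent to be screened and verify all inclusion criteria". Later in the same section, the reference is to the exclusion list: "YYA who screen ineligible (see section 4.2 for exclusion criteria) will be informed at the conclusion of the screener".

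**The concern.** The exclusion bullet appears intended as the mirror image of the inclusion bullet. If it were, a person would be excluded only by failing both conditions. Because it is joined with OR, failing either one is enough, and applying the two lists together turns an either/or rule into a requirement for both.

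Two kinds of people are caught. One claims a listed identity, for example gender non-conforming, but reports a current gender that matches birth sex. The other has a current gender that differs from birth sex but uses none of the three listed labels. Each meets 4.1.3 and each is ruled out by 4.2.3.

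What is at stake is the definition of the trial's population. Someone programming the screener, reviewing charts for potential eligibility under section 4.3, or monitoring protocol compliance under section 7.7 would reach a different answer for such a person depending on which list was followed.

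**Working it through.** The plan states no figure on this point, so the check is one of logic.

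**Inputs.** Let A mean that the person claims one of the three listed identities, and B that birth sex and current gender differ. The two genders matching is then not-B.

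- Inclusion (4.1.1 to 4.1.3, and the Abstract): A or B.
- Exclusion as written (4.2.1 to 4.2.3): not-A or not-B.
- True negation of the inclusion rule: not-(A or B) = not-A and not-B.

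**All four combinations.**

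| A | B | Meets inclusion | Excluded as written | Both included and excluded | Excluded with AND |
|---|---|---|---|---|---|
| yes | yes | yes | no | no | no |
| yes | no | yes | yes | **yes** | no |
| no | yes | yes | yes | **yes** | no |
| no | no | no | yes | no | yes |

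Three combinations meet inclusion. Two of those three are also excluded, and only A and B together passes both lists. With AND, the exclusion is the exact complement of inclusion: no combination is in both lists and none is in neither.

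**An alternative reading.** One could let the opening negative govern the whole bullet, so that it excludes a person for whom neither the listed identity nor the match holds: not-(A or not-B) = not-A and B. This does not rescue the text. It still excludes the person with B only, who meets inclusion. It also fails to exclude the person with neither A nor B, whom the bullet should catch.

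**Comparison with neighbouring bullets.** Other bullets in 4.2.3 negate their inclusion counterparts correctly. The age range of 15 to 24 becomes below 15 or above 24. The requirement to read and speak English becomes failing either or both. The gender bullet departs from that pattern.

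**Which list governs.** Section 4.4 says that the screener verifies inclusion, which points to the 4.1 rule. It then cites section 4.2 for those who screen ineligible, which points to the conflicting one. Nothing in the section says which prevails.

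**The case against.** The strongest reply is that the intent is plain and the practical risk small. The either/or rule stands in the Abstract and in all three inclusion lists, and most of 4.2.3 only restates 4.1.3 in negative form. A sensible reader would take the bullet as a loosely worded negation. Section 4.4 also routes every potential participant through one online survey. When staff screen in person, by phone or by video, they read out that survey's questions and enter the answers in it. If the survey codes the inclusion rule, the faulty bullet has no effect at screening.

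Much of this stands. This is a drafting slip and not a deliberate narrowing of the population. It does not remove the contradiction, because the same section cites 4.2 for ineligibility and the survey logic is not in the documents.

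Three stronger readings are tempting, and the documents support none of them.

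- A reader might infer that sites have turned eligible people away. That depends on the unseen survey logic. Whether a gender non-conforming person is caught also depends on how current gender is asked: someone who gives gender non-conforming as their current gender could satisfy both conditions.
- A reader might want a count of those affected. The documents do not give the share who qualify by one route only, so any number would be a guess.
- A reader might infer that single-route participants risk removal after randomisation. Section 8.4 gives general discretion over discontinuation but does not name failure of a gender criterion. Sections 10.3.2 and 10.4 contain no rule dropping ineligible participants from the analysis.

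**Conclusion.** The point holds as a contradiction within an operative eligibility rule. The first bullet of 4.2.3, and its copies in 4.2.1 and 4.2.2, give the wrong result if followed as written: two of the three combinations that meet inclusion are also excluded. This conclusion needs no assumption beyond reading OR in its ordinary sense, and the other possible reading of the sentence also fails.

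The practical effect is unknown. It could be nil if the screener codes 4.1.3, and it cannot be sized from the documents if the screener copied 4.2.3. The target of 275, the power statement in 10.2.2 and the analysis method in 10.3.2 are not directly affected. The error still deserves correction, because it sits in the criterion that says who the trial is about and because correcting it costs almost nothing.

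**What to change.** Replace OR with AND in the first bullet of 4.2.1, 4.2.2 and 4.2.3. Alternatively, delete the three bullets, since they only restate inclusion in negative form. Either change removes the conflict. Then confirm that the online screener codes the either/or rule of 4.1.3 for the RCT.

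The cost is one word in each of three bullets, made in a protocol amendment, plus one check of the screener logic. Sample size, randomisation and analysis need no change.

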4.3 Recruitment

The following recruitment strategies will be utilized to ensure enrollment targets are met and a diversity of participants are enrolled. 1) Online Recruitment: Online banner ads targeting trans YYA will be placed through geo-mapping on websites and social media in SRV cities. We will also distribute digital flyers to community leaders who will inform their email distribution lists with information on how to participate in the study. Additional online recruitment may also be conducted, including but not limited to recruiting via online social media outlets (e.g., Facebook,

Instagram, Snapchat, etc.). 2) SRV and other Community-based Outreach: flyers and posters will be created and distributed in SRVs and other community-based organizations and clinic settings that cater to trans YYA. The flyers and posters will contain details about how to contact a SRV Research Assistant for further information or how to screen online for the RCT. 3) Peer Referral: Participants who screen eligible for the RCT will be asked to refer friends who are also trans YYA. For the RCT, we will follow respondent-driven sampling (RDS) methods and use a long-chain referral method to supplement recruitment, especially with the adolescents (15-17) who may be harder to reach than young adults (18-24). 4) Clinic-based recruitment may include reviewing medical charts of existing patients for potential eligibility, or referrals from other providers in the clinic. 5) Former participants who have previously given consent to be contacted for future research may also be directly contacted for recruitment and screening. 6) Print Media: Ads will be placed in print media that trans YYA read. 7) Street- and Venue-based Outreach: Research Assistants will utilize a semi-structured time-space sampling methodology to conduct street- and venue-based outreach identified through the Trans Youth Community Advisory Board and ongoing community mapping at locations where young trans YYA congregate. Research Assistants will be trained on appropriate outreach strategies, how to build and maintain ongoing trust and rapport, and how to conduct confidential screening.

4.4 Screening

All potential participants (whether recruited online, in-person or over the phone) will complete an online screening survey to obtain consent/assent to be screened and verify all inclusion criteria. Screening may occur on the same day as enrollment or beforehand. The online screening survey will begin with a script that will be read by participants to explain the purpose of screening and clarify that if they are eligible, they will be invited to participate in the study. The script will also provide general information about the research study, the nature of the screening questions and related potential risks, the approximate length of the screening (~5 minutes), the confidentiality of the screening information, the use of any screening information obtained, the ability to skip any questions or withdraw at any time, and contact information of key study personnel. After reading this screening script, participants will be asked if they are interested in participating and agree to voluntarily complete the screening procedure. Participants will electronically indicate their agreement and then take the screening survey.

SRV staff may also screen participants using the online screener in person, over the phone, or over a teleconferencing platform such as Zoom or a comparable platform. The SRV staff will obtain verbal consent from the participant to screen, read the screening questions from the online survey to the participant, and record the participant's responses in the online screener.

The online survey is hosted on Alchemer and we will use SSL encryption for transfers of information online and data will be stored in the secure, HIPAA-compliant servers of Alchemer. The Emory AC team maintains a business partner HIPAA agreement with Alchemer. For those who meet eligibility criteria, the survey will ask if they are willing to provide their first name, e-mail, and a phone number. Potential participants who do not meet eligibility criteria will be asked if they would like to be contacted about other research studies and, if so, to provide contact information.

The Analytic Core will securely share the contact information of eligible participants with SRV sites via a secure Box or Microsoft OneDrive account. SRV staff will enter the eligible participant into SMART for scheduling and contact participants to schedule an in-person visit at the SRV or an online enrollment visit. Study staff also have the option of scheduling and completing some study visit activities in person and some of the study visit activities online to provide flexibility during the COVID-19 pandemic and afterwards and to be responsive to participant needs.

YYA who screen eligible and provide contact information will be contacted by SRV staff and provided with information about the date and time of the focus group (in Phase 1) or to schedule an in person or online baseline enrollment visit (in Phase 2). An email will be sent to potential focus group participants immediately after they are scheduled for the focus group that includes the focus group date, time, location and staff contact information. Potential focus group participants will be sent a reminder three days prior to the focus group, as well as on the day of the focus group.

YYA who screen ineligible (see section 4.2 for exclusion criteria) will be informed at the conclusion of the screener that they are not eligible for the study.

4.4.1 Contact Info

Once the participant is consented/assented, designated site study staff will complete a Locator/Contact Information Worksheet with the participant and/or enter the participant's contact information directly into SMART Web during the enrollment visit. Participants will be asked to provide a working phone number and/or valid email address through which they can be reached. Participants will also be asked to provide social media contact information. Participants will also be asked to provide valid contact information for two family members and/or friends who can be called in the event the participant cannot be reached by phone or email. Participants will be asked if messages can be left at the numbers provided. Study staff will not leave messages unless expressly permitted to do so by the participant which also will be documented on this form. If permission is given to leave messages, site study staff will assure participants that messages left with a family member or friend will only ask the participant to contact study staff and will not include any protected health information or information related to study participation. For participants randomized to the eCoaching intervention, the eCoaches based at PRIDE will ask participants in the eCoaching intervention to provide them with contact information similar to what the participant provided to the SRV when they were enrolled.

